5.2.3 Dose modification of apatinib mesylate

Dose modifications caused by apatinib-related toxicities include the following: treatment interruption (no more than 28 days), dose reduction (to 375 mg qd or 250 mg qd, depending on the initial dose of apatinib), and permanent discontinuation.

The treatment may be delayed and the dose be reduced for Grade ≥ 3 hematologic toxicity or ≥ 2 non-hematologic toxicity; for non-hematologic toxicity, manageable nausea and vomiting, and fever (below 38 $^{\circ}\text{C}$) of determined cause, active symptomatic treatment can be administered first. There is no need to immediately delay the treatment or reduce the dose.

In case of apatinib-related toxicity, administration should be delayed until recovery, and then the original dose should be resumed or the dose should be reduced by one dose level. The minimum dose allowable is 250 mg/d. If the dose is still intolerable at the reduced dose of 250 mg/d, apatinib should be permanently discontinued (refer to [Table 9](#) for the recommended dose modification method). Dose increase of apatinib is not allowed during the study period.

Table 9. Recommended dose modification of apatinib

Apatinib-Related Toxicities	Grade	Dose Delay or Not	Criteria for Resuming	Dose Modification Method	Criteria for Discontinuation
Hematologic Toxicity	Grade 1-2	No	—	—	—
	Grade 3	Yes	Until the toxicity recovers to Grade ≤ 2	Resume at original dose	Apatinib interruption for more than 28 days
	Grade 4		Until the toxicity recovers to Grade ≤ 2	Reduce the dose by one level	
Non-Hematologic Toxicity	Grade 1	No	—	—	—
	Grade 2 (last for ≥ 7 days)	Yes	Until the toxicity recovers to Grade ≤ 1	Resume at original dose	Apatinib interruption for more than 28 days
	Grade 3	Yes	Until the toxicity recovers to Grade ≤ 1	Reduce the dose by one level	
Hypertension	Grade 3 (after corrective treatment)	Yes	Until the toxicity recovers to Grade ≤ 1	Reduce the dose by one level	Apatinib interruption for more than 28 days
Proteinuria (without significant increase in blood creatinine)	Grade 3 (24-h urine protein quantification)	Yes	Until the toxicity recovers to Grade ≤ 2	Reduce the dose by one level	Apatinib interruption for more than 28 days

Apatinib-Related Toxicities	Grade	Dose Delay or Not	Criteria for Resuming	Dose Modification Method	Criteria for Discontinuation
Hand-and-Foot Syndrome	Grade 3	Yes	Until the toxicity recovers to Grade ≤ 1	Reduce the dose by one level	Apatinib interruption for more than 28 days
Headache	Grade 2 (last for ≥ 7 days) or Grade 3	Yes	Until the toxicity recovers to Grade ≤ 1	Reduce the dose by one level	Apatinib interruption for more than 28 days

In this study, the minimum dose of apatinib allowable is 250 mg/d. If the subjects still cannot tolerate the dose of 250 mg/d, apatinib should be permanently discontinued.

For subjects with gastrointestinal perforation, wound dehiscence needing clinical management, fistula, severe hemorrhage, nephrotic syndrome or hypertensive crisis, apatinib should be permanently discontinued.

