	Grade 3-4	Discontinuation	Discontinuation
Immune-Related Hypophysitis	Grade 2-3	The SHR-1210 treatment may continue after the toxicity reduces to Grade 0-1 and the hormone replacement therapy starts.	Toxicity has not resolved by 12 weeks after the last dose, or the corticosteroid dose cannot be reduced to prednisone 10 mg/day (or equivalent) or lower within 12 weeks after the last dose.
	Grade 4	Discontinuation	Discontinuation
Renal Failure or Nephritis	Grade 2	Toxicity reduced to Grade 0-1	Toxicity has not resolved by 12 weeks after the last dose, or the corticosteroid dose cannot be reduced to prednisone 10 mg/day (or equivalent) or lower within 12 weeks after the last dose.
	Grade 3-4	Discontinuation	Discontinuation
Infusion reactions	Grade 2 ^b	Symptoms disappeared	Discontinue the drugs if the symptoms recur after adequate premedication.
	Grade 3-4	Discontinuation	Discontinuation
Other T-related toxicities ^c	Grade 3	Toxicity reduced to Grade 0-1	Toxicity has not resolved by 12 weeks after the last dose, or the corticosteroid dose cannot be reduced to prednisone 10 mg/day (or equivalent) or lower within 12 weeks after the last dose.
	Grade 4	Discontinuation	Discontinuation

Treatment should be discontinued if any grade ≥ 3 treatment-related AE recurs (grade ≥ 2 pneumonia) or any life-threatening event recurs.

- a) For subjects with liver metastasis and grade 2 AST or ALT increased at baseline, if the AST or ALT increased $\geq 50\%$ from baseline persists for at least 1 week, the treatment shall be discontinued.
- b) If the symptoms resolve within 1 hour after dechallenge, and the infusion can be resumed at 50% of the initial infusion rate. Otherwise, the treatment can only be resumed until symptoms are fully resolved. Premedication is required prior to the next dose. Refer to section 5.6.2 "Recommendations on infusion reaction management" for further management.

- c) For subjects with intolerable or persistent grade 2 treatment-related AEs, the investigator may consider interrupting SHR-1210 treatment if appropriate, and the treatment should be discontinued if toxicity fails to decrease to Grade 0-1 within 12 weeks after the last dose.

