5.3 Duration of Treatment

All subjects should continue to receive the study treatment until progressive disease, intolerable toxicity, voluntary treatment discontinuation or study withdrawal by the subject, or discontinuation determined by the investigator.

SHR-1210 is an immune checkpoint inhibitor and according to the experience of similar drugs, some subjects may experience delayed or early pseudo progression after receiving immunotherapy drugs. For subjects in the treatment group experiencing progressive disease (PD) for the first time, they may continue with the SHR-1210 treatment if they meet the criteria in section 4.6 Criteria for Continuing Treatment Beyond Disease Progression. Subjects who do not have progressive disease or intolerable toxicities may continue the SHR-1210 treatment for no more than 24 months. Subjects who do not have progressive disease after 24-month treatment may continue the apatinib monotherapy according to the prescribing information of apatinib.

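### Table 9 gives no rule for Grade 4 non-hematologic apatinib toxicity, so the written rule for Grade 4 is looser than for Grade 3 and does not exclude full-dose re-challenge

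*Protocol*

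**What the plan says.** Protocol section 5.2.3 has three layers.

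- **General text.** Besides stopping apatinib for good, the available tools are "treatment interruption (no more than 28 days), dose reduction (to 375 mg qd or 250 mg qd, depending on the initial dose of apatinib"). The trigger sentence begins "The treatment may be delayed and the dose be reduced for Grade" and reaches hematologic toxicity of Grade 3 or above and non-hematologic toxicity of Grade 2 or above, so it includes Grade 4. The resumption sentence reads: "administration should be delayed until recovery, and then the original dose should be resumed or the dose should be reduced by one dose level".
- **Table 9.** It gives recommendations by type and grade of toxicity. Hematologic toxicity has a Grade 4 row. The non-hematologic rows stop at Grade 3.
- **Absolute stops.** After the table: "If the subjects still cannot tolerate the dose of 250 mg/d, apatinib should be permanently discontinued". The permanent-stop list is gastrointestinal perforation, "wound dehiscence needing clinical management, fistula, severe hemorrhage, nephrotic syndrome or hypertensive crisis, apatinib should be permanently discontinued". That makes six events, defined by type and not by grade.

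The starting dose under version 6.0 is 375 mg once daily and the lowest permitted dose is 250 mg/d.

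**The concern.** A dose table normally becomes stricter as grade rises. Here the Grade 3 instruction is specific, and at Grade 4 the reader falls back on a sentence that offers the full dose as one of two options. Table 13, the protocol's scale for events that CTCAE does not list, describes Grade 4 as life-threatening.

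Two things are at stake. A subject could be re-exposed at full dose after such an event without breaching section 5.2.3. And two sites could handle the same event differently, at 375 or 250 mg/d. The case is not hypothetical: item 1 of the version 6.0 changes lists an apatinib-related Grade 4 skin toxicity, which is not on the permanent-stop list.

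**Working it through.** No figure in the plan is to be reproduced. The check is a reading of section 5.2.3 grade by grade, followed by a search for any other rule that fills the gap.

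**Step 1. Table 9 by grade**

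| Toxicity | Grade 2 | Grade 3 | Grade 4 |
|---|---|---|---|
| Hematologic | no delay | hold to ≤ 2, original dose | hold to ≤ 2, one level down |
| Non-hematologic, general | if ≥ 7 days: hold to ≤ 1, original dose | hold to ≤ 1, one level down | no row |
| Hypertension | no row | after corrective treatment: hold to ≤ 1, one level down | no row |
| Proteinuria | no row | hold to ≤ 2, one level down | no row |
| Hand-and-foot | no row | hold to ≤ 1, one level down | no row |
| Headache | if ≥ 7 days: hold to ≤ 1, one level down | hold to ≤ 1, one level down | no row |

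There is one Grade 4 row for hematologic toxicity and none for non-hematologic. The Grade 3 rows cannot safely be read as Grade 3 or above. The same section writes ≥ where it means it, and the hematologic block gives Grade 4 its own row with a different action.

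**Step 2. What governs a Grade 4 non-hematologic event off the stop list**

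The two general sentences. Together they require delay until recovery, permit reduction, and leave the original dose open. For Grade 3, Table 9 fixes both the recovery grade and the dose. For Grade 4, neither is fixed.

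**Step 3. Whether another rule closes the gap**

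- The 28-day limit does not reach an event that recovers sooner.
- The 250 mg/d floor acts only once that dose is not tolerated.
- Section 5.3, "All subjects should continue to receive the study treatment until progressive disease, intolerable toxicity", and the criteria in sections 4.5, 4.5.1 and 4.5.2 (including the investigator's other reasons) depend on judgment and name no grade.
- The sentence under Table 7 that stops treatment if a severe related event recurs, "or any life-threatening event recurs", sits in the SHR-1210 section. Even if carried over to apatinib, it acts only at recurrence, that is, after re-challenge.
- Appendix 4's rash guidance concerns the immunotherapy.
- Section 5.5 refers to package inserts for contraindications and precautions, and sets no study dose rule.

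None of these sets a Grade 4 action or rules out the original dose for an event that resolves within 28 days.

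**Step 4. What the protocol does for other drugs**

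Table 7's catch-all row for SHR-1210, "Other T-related toxicities", discontinues at Grade 4. Table 8 stops capecitabine at Grade 4 or, if the investigator sees benefit, holds to Grade 0-1 and resumes at 50%.

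**Step 5. The numbers that exist**

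- Reported: 1 Grade 4 skin toxicity among 11 patients at 500 mg/d, counted as one patient. 1/11 = 9.1%. Exact 95% interval: lower limit Beta(0.025; 1, 11) = 0.2%, upper limit Beta(0.975; 2, 10) = 41.3%.
- Dose left open from a 375 mg start: 375 × 21 = 7875 mg against 250 × 21 = 5250 mg per cycle, a difference of 125/375 = one third.
- From a 500 mg start: 500 × 21 = 10500 mg against 7875 mg, a difference of 125/500 = one quarter.

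**The case against.** The best defence is that the resumption sentence belongs to a paragraph that sends the reader to Table 9, so its two options can be read as a summary of the table. The table escalates (non-hematologic Grade 2 resumes, Grade 3 reduces; hematologic Grade 3 resumes, Grade 4 reduces), and a sensible investigator would extend that to Grade 4. Investigators may also withdraw a subject for adverse events, and life-threatening events are reported as SAEs within 24 hours. This is a fair account of likely practice. But it relies on inference where the table is silent, while the only text that does apply offers the full dose.

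It is also fair that the protocol has no uniform Grade 4 norm. The oxaliplatin rules in section 5.2.2 cover only neurotoxicity, renal injury and hematologic toxicity. Table 7 lets SHR-1210 resume after Grade 3-4 hyperglycemia once the subject is stable. The comparison with Tables 7 and 8 therefore shows that a Grade 4 rule is practicable, not that the protocol always has one. Table 13's description applies only to events outside CTCAE, and section 7.2.7 lists a Grade 4 event defined by laboratory values (amylase or lipase), so not every Grade 4 event need be an emergency.

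Three stronger readings are tempting, and the documents do not support them:

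- **That Table 9 advises carrying on at Grade 4.** The table writes No where it means no delay. At Grade 4 it is silent, and the text requires delay until recovery.
- **That the reported skin toxicity was mishandled or re-challenged.** Nothing says so.
- **That the number of full-dose re-challenges can be estimated.** That needs the Grade 4 rate at 375 mg/d, the fraction recovering within 28 days without being stopped, and the fraction resumed at full dose. The documents give none of these.

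**Conclusion.** The point holds as a gap in a safety rule. For Grade 4 non-hematologic apatinib toxicity outside the six permanent-stop events, section 5.2.3 requires a delay but fixes neither the recovery grade nor the resumption dose, so it is looser than the rule for Grade 3. Full-dose re-challenge after recovery within 28 days is not excluded. The remaining stopping rules are judgment-based, event-specific or act only after recurrence.

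Its documented size is one event in 11 patients at 500 mg/d, a dose since reduced for poor tolerability. The interval is very wide and should not be carried over to 375 mg/d. The conclusion rests on Table 9 having been read intact; its non-hematologic rows run on without a visible break into the hypertension row.

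A correction is worth making because the stated text expressly permits the less safe option and the change is cheap. It is not a threat to the trial's validity: the ORR analysis, alpha and power rules do not depend on it.

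**What to change.** 1. Add a Grade 4 row to the non-hematologic block of Table 9: permanently discontinue apatinib or, only if the investigator judges continued benefit, hold until Grade 1 or lower and resume one dose level down, never at the original dose. A subject already at 250 mg/d discontinues. Table 8's Grade 4 entry for capecitabine is a ready model.
2. State that this row also governs Grade 4 of the hypertension, proteinuria, hand-and-foot and headache rows, where the grading scale has a Grade 4. Otherwise it is unclear which recovery grade applies, since proteinuria resumes at Grade 2 or lower.
3. Amend the resumption sentence in the text so that the choice between original dose and reduction follows Table 9 by grade. Adding the row alone would leave the permissive sentence in place.

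The cost is one row and one sentence in an amendment, with no extra patients, visits or procedures. The downside is slightly less investigator discretion and some lost apatinib exposure after Grade 4 events.

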5.3 Duration of Treatment

All subjects should continue to receive the study treatment until progressive disease, intolerable toxicity, voluntary treatment discontinuation or study withdrawal by the subject, or discontinuation determined by the investigator.

SHR-1210 is an immune checkpoint inhibitor and according to the experience of similar drugs, some subjects may experience delayed or early pseudo progression after receiving immunotherapy drugs. For subjects in the treatment group experiencing progressive disease (PD) for the first time, they may continue with the SHR-1210 treatment if they meet the criteria in section 4.6 Criteria for Continuing Treatment Beyond Disease Progression. Subjects who do not have progressive disease or intolerable toxicities may continue the SHR-1210 treatment for no more than 24 months. Subjects who do not have progressive disease after 24-month treatment may continue the apatinib monotherapy according to the prescribing information of apatinib.

5.4 Drug Management, Dispensation, Return and Disposal

Designated personnel are responsible for management, dispensation, and return of study drugs. The investigator must ensure that all study drugs are used by enrolled subjects only and the dose and route of administration comply with Section 5.1.4. Remaining or expired drugs should be returned to the sponsor or destroyed at the study center according to the specified procedures, and may not be used for non-participants.

During distribution of the drugs, a drug receipt form should be signed by both parties in duplicate, one copy for the study center and one copy for the sponsor. When returning remaining drugs and empty packaging, both parties must sign the drug retrieval form. The dispensation and return of every drug should be immediately documented on designated forms.

The CRA is responsible for monitoring the supply, use, and storage of study drugs, and disposal of remaining medications.

● **Disposal of study drugs**

The sponsor or authorized personnel is responsible for disposing the study drugs. Drug disposal should be well documented.

5.5 Recording of concomitant medications and concomitant treatments

Concomitant medications/treatments refer to any drugs/treatments that are given for the interest of subjects as determined by the investigator.

All concomitant medications, blood products, and non-drug interventions (eg., paracentesis) that are given to the subjects from 30 days prior to the first dose to the end of the safety visit must be strictly documented in the CRF according to GCP requirements.

Prohibited medications and vaccines specified in the study protocol are strictly prohibited during the entire course of study. If the subject develops a comorbidity requiring treatment with a prohibited drug, the investigator should consult with the sponsor before discontinuing the study treatment or using the prohibited drug. Whether the subject will continue the study treatment or receive a prohibited drug should be jointly decided by the investigator, the sponsor, and the subject.

In addition to the following contents, for subjects who receive apatinib mesylate, capecitabine and oxaliplatin treatment, the latest package insert of marketed drugs or medical practices regarding contraindications and precautions shall be also taken for reference.

5.5.1 Other anti-tumor treatments or investigational drugs

Other anti-tumor treatments not specified in the protocol are not permitted while subjects are receiving study treatment, including CDFA (NMPA)-approved Chinese herbal preparations for anti-tumor treatments (see [Appendix 6 Prohibited Traditional Chinese Medicines During the Study Period](#)) and immunomodulators (including but not limited to interferon, interleukin-2, and thymosin).

Participation in other drug/medical device clinical studies is not permitted.

Other systemic anti-tumor treatments such as chemotherapy, molecular targeted therapy, hormone therapy, immunotherapy, biological therapy, and radiotherapy are not permitted.

Subjects can receive bisphosphonate for the treatment of bone metastases. If systemic treatment or local analgesia is not effective in controlling painful lesions of bone metastases, a small area of palliative radiotherapy (the area of the radiotherapy must be < 5% of the bone marrow region, and the percent bone marrow in human is shown in [Appendix 5 Percent Bone Marrow Content in Human Skeleton](#)) is allowed.

Palliative treatment of local lesions that may cause obvious symptoms is permitted. For example, local radiotherapy or surgery may be considered for bone lesions that cause pain. However, the following criteria must all be met. It is also recommended to consult with the sponsor prior to starting palliative treatment.

- 1) The investigator must assess whether there is progressive disease in subjects who require local treatment due to symptom exacerbations during the study;
- 2) Subjects with progressive disease have to meet the criteria for continuation of treatment beyond progression;
- 3) The locally treated lesions should not be the target lesions.

5.5.2 Vaccines

Live attenuated vaccines should not be given within 4 weeks before the first dose or during the study period. Subjects who are expected to require live attenuated vaccines during the study period are not recommended for enrollment.

Inactivated vaccines for preventing infectious diseases, such as pneumonia, influenza, are permitted. Any other vaccines should be discussed with the sponsor before administration.

5.5.3 Immunomodulators and corticosteroids

Concomitant immunosuppressive therapy is not permitted (except when treating treatment-related adverse events).

Concomitant immunostimulants are not permitted (except when treating treatment-related AEs).

Long-term, systemic use of corticosteroids is prohibited. The use of corticosteroids for ≤ 1 week as premedication for chemotherapy or contrast media allergies as specified in the package insert is permitted. Systemic treatment with corticosteroids is permitted for individual subjects after discussing with the sponsor. Short term (≤ 3 weeks) use of corticosteroids for non-autoimmune diseases is permitted (such as delayed allergic reactions caused by contact allergens).

Emergency use, topical application, inhalation, eye drops, or local injections of corticosteroids are permitted. Physiological replacement doses (such as adrenal replacement doses) of systemic corticosteroids (≤ 10 mg/d of prednisone or equivalent) are permitted.

5.5.4 Hematopoietic growth factor and blood transfusion

Any granulocyte colony-stimulating factor, erythropoietin, thrombopoietin, and other hematopoietic stimulation factors, as well as blood transfusion and blood products (eg., albumin) are prohibited as primary prophylaxis before treatment. However, these treatments are allowed for treating AEs.

5.5.5 Anti-inflammatory treatment

Anti-inflammatory medications or narcotic analgesics can be given if there are no known or foreseeable drug interactions and if these drugs are not prohibited in the protocol.

5.5.6 Medications to be used with caution in subjects receiving apatinib during the study

Drugs that may affect the metabolism of apatinib or prolong QT interval should be used with caution in subjects in cohort 2 (SHR-1210 + apatinib).

- Drugs that may have drug-drug interactions with apatinib mesylate

In vitro metabolic enzymes studies have shown that apatinib is mainly metabolized by CYP3A4. When apatinib is used concomitantly with strong inhibitors of CYP3A4 (itraconazole, clarithromycin, voriconazole, telithromycin, saquinavir, and ritonavir), the plasma concentration of apatinib may rise up. When apatinib is used concomitantly with CYP3A4 inducers (dexamethasone, phenytoin, carbamazepine, rifampicin, phenobarbital, and rifapentine), the plasma concentration of apatinib may decrease. When other combined medications are needed, it is recommended to choose alternative drugs that do not inhibit or induce CYP3A4. If a strong inducer or inhibitor of CYP3A4 enzyme must be used concomitantly, it is necessary to consider whether to modify the dose based on clinical observation.

- Drugs that prolong the QT interval of the heart

As tinib drugs may cause toxicities of prolonged QT interval in clinical applications, drugs that may prolong the QT interval should be used with caution during the study. These mainly include, but are not limited to, the following categories of drugs:

- ◆ Antibiotics: fluoroquinolones: sparfloxacin, gatifloxacin, levofloxacin, moxifloxacin, ofloxacin, ciprofloxacin; macrolides: erythromycin, clarithromycin, telithromycin, azithromycin, roxithromycin, and metronidazole.
- ◆ Antiarrhythmics: quinidine, procainamide, disopyramide, flecainide, propafenone, amiodarone, dronedarone, sotalol, dofetilide, and ibutilide.
- ◆ Drugs used to relieve angina: ranolazine and ivabradine.
- ◆ Antipsychotics: risperidone, fluphenazine, droperidol, haloperidol, thioridazine, pimozide, olanzapine, and clozapine.
- ◆ Antifungal drugs: voriconazole and posaconazole.
- ◆ Antimalarial drugs: mefloquine and chloroquine.
- ◆ Antihistamines: terfenadine, astemizole, and hydroxyzine.

- ◆ Gastrointestinal drugs: antiemetics: ondansetron, granisetron, dolasetron, droperidol (0.625-1.25 mg may be a safe dose), hydroxyzine; prokinetics: cisapride, domperidone, metoclopramide.
- ◆ Antidepressants: amitriptyline, imipramine, clomipramine, dosulepin, and doxepin.

